We hypothesize this rehabilitation strategy will also be successful in human subjects. The proposed project aims to translate animal hemianopia research to a noninvasive rehabilitation system for use by human visual hemianopia patients. The specific objectives of the program can be enumerated as follows:

Specific Aim 1: Determine the efficacy of an intervention using cross-modal stimulation training to restore visual function in homonymous hemianopia patients.

Specific Aim 2: Assess the long-term effects of rehabilitation through follow-up visits after the completion of rehabilitation.

Methods and Measures

Design

This study will test a rehabilitation technique for treating visual hemianopia and compare results against measures from patients pre-intervention. We will recruit all interested patients with visual hemianopia and will assess visual field, visual capabilities, quality of life, and brain images as part of our research measures.

Setting

Rehabilitation training sessions and progress tests will be performed on the Wake Forest Baptist Medical Center Campus and in subjects' homes. Since administering the Humphrey visual field test requires specific equipment, subjects will visit an optometrist's office for these tests. Subjects will perform the remaining visual tests on the Wake Forest Baptist Medical Center Campus.

Subjects selection criteria

- **Inclusion Criteria**
 - Adult volunteers diagnosed with homonymous visual hemianopia / hemianopsia (ages 18-99)
 - MRI or CT scan demonstrating lesion in the occipital lobe of the brain and/or affecting white matter tracts that provide visual input to the occipital lobe of the brain
 - Brain injury due to ischemic or hemorrhagic causes that occurs after age 18 and at least 6 months prior to screening visit
 - Demonstration of good fixation on visual training task
- **Exclusion Criteria**
 - Volunteers who are unable to complete the study tasks or understand instructions
 - Subjects that are not able to provide written consent or verbal assent
 - Subjects who are not available to complete all rehabilitation sessions
 - Physical, neurological or mental disability that would interfere with study intervention
 - Concurrent participation in "vision therapy" other than standard occupational or physical therapy

- **Sample Size**

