The goal of this project is to obtain proof the rehabilitation technique has the potential to be successfully translated to humans. To achieve this goal, we will recruit a sample size of 10 hemianopia subjects in this study in hopes of having at least 5 participants complete all study sessions. This study is exploratory; the findings from this study will be used to design future studies. The observed treatment response pattern will be reported, and those data used for informed estimates of incidence for future research. Prior animal model studies demonstrated a high success rate in the rehabilitation strategy, with 100% of 11 hemianopic cats regaining visual field. Assuming that 80% of subjects will have a successful result, using n=5 subjects will allow for estimation of a 95% confidence interval with width 0.35 units either side of the estimate [22].

Interventions and Interactions

Interventions

Cross-Modal Visual Auditory Rehabilitation - Cross-modal visual auditory rehabilitation is based on the rehabilitation paradigm derived from previous animal model studies. The rehabilitation will be carried out using a virtual reality rehabilitation (VR) system. The rehabilitation system uses a customized commercial wireless VR headset, the Samsung Gear VR, to run custom-made rehabilitation software.

The cross-modal rehabilitation software provides a gray colored, neutral environment for patients, with minimal distractions from rehabilitation. Subjects will be asked to fixate on a colored fixation spot in the center of the visual field for 1 second before being randomly presented with either a visual stimulus in the normal intact visual field or a spatiotemporally coincident audio-visual stimulus in the hemianopic side. Auditory-visual stimulus and visual stimulus will be presented at a ratio of 9:1 respectively. The design of the fixed, predictable timing and 9:1 ratio will help subjects shift their attention to the blind field.

[figure not shown]

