During this visit, baseline measurements for subjects will be obtained. Subjects will undergo a peripheral visual field test and be asked to complete 2 quality of life questionnaires: the National Eye Institute Visual Function Questionnaire (NEI VFQ-25) and the Veterans Affairs Low Vision Visual Function Questionnaire (VA LV VFQ-48). Subjects are expected to spend up to 2 hours for this visit.

(Optional) Study Session 2: Pre-Intervention Test - Humphrey Visual Field Test (1 hour)

Subjects will report to an optometrist, who will administer the Humphrey Visual Field Test, using a size V stimulus. This visit will be separate from the other pre-intervention tests due to the special equipment needed for the Humphrey Visual Field Perimetry. This visit is expected to take up to 1 hour. This visit may be omitted if subjects have a recent Humphrey Visual Field Perimetry test result and gives the study team permission to view and keep a copy of the result.

Study Sessions 3 – 32: Cross-Modal Rehabilitation Training (30 minutes each day)

Each cross-modal rehabilitation training session will take place either on the Wake Forest Baptist Medical Center Campus or in subjects' homes, if subjects find traveling to the Wake Forest campus to be too difficult to do daily. For patients who are performing rehabilitation at home, the study team will regularly call and check-in with the subject in order to make sure the patient is not experiencing any problems. The VR rehabilitation system will send data such as duration of rehabilitation and progress test results through a cellular network, in order to monitor compliance and track rehabilitation progress. The data will only be linked to a study identifier to maintain privacy. Initial rehabilitation sessions will be done at the Wake Forest Baptist Medical Center campus to ensure subjects understand how to use the rehabilitation device and are capable of performing rehabilitation at home.

In each rehabilitation session, subjects will sit down, put on a virtual reality headset with a pair of headphones, and use a button on a handheld controller to interact with the rehabilitation system. In order to make sure subjects are correctly performing rehabilitation, the headset may be outfitted an eye tracking system consisting of a camera and low intensity infrared lights to collect data on patient's eye movements.

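### The frame test has a single pre-training baseline in a one-arm before/after design, so practice gain is included in the estimated effect; a repeat before the first training trial would give a cheap, rough check.

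*Combined protocol and SAP*

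**What the plan says.** Under Design, the study tests the technique in one group and will "compare results against measures from patients pre-intervention". Specific Aim 1 is to "Determine the efficacy of an intervention using cross-modal stimulation training to restore visual function in homonymous hemianopia patients". The Sample Size section takes a more modest view: "This study is exploratory; the findings from this study will be used to design future studies".

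Outcome Measure(s) names two primary field measures, the Humphrey visual field (HVF) and the peripheral frame test, compared before and after treatment. The frame test is given once before training, in session 1: "Subjects will undergo a peripheral visual field test". HVF is done once in optional session 2, and a recent existing result may replace it. The Analytical Plan assesses improvement by a two-way ANOVA on hemianopic-side detection percentages in the frame test, before against after.

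The document gives no repeat baseline, no test-retest estimate and no success threshold for either primary test. On where training starts, the section on sessions 3-32 says "Initial rehabilitation sessions will be done at the Wake Forest Baptist Medical Center campus".

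**The concern.** In a one-arm comparison, whatever changes between the two tests is read as the effect of training. Practice is a plausible part of that change. Between the tests a subject completes about 30 × 200 = 6,000 training trials, pressing a button on detecting a stimulus, which is also the response that the frame test asks for. Subjects who are not comfortable with the headset may train on the frame device itself. Greater ease with the task, or a looser criterion for pressing, would pass straight into the before/after difference.

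A second issue concerns individuals. The sample size argument is built on the proportion of subjects with a successful result, and the observed response pattern is meant to inform later studies. With few trials per test and no threshold for success, some unchanged subjects may look improved.

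**Working it through.** **The plan's own figure.** For an 80% success rate and n = 5, the Wald half-width is 1.96 × √(0.8 × 0.2 / 5) = 0.3506, which reproduces the stated 0.35. The interval runs from 0.45 to 1.15; the exact interval for 4 of 5 is 0.28 to 0.99. Either covers sampling error in the success rate only, not practice or error in classifying a subject as a success.

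**Trials per frame test** (Peripheral Visual Field Test). 5 azimuths × 5 trials = 25 on the hemianopic side, 25 on the intact side, plus 5 with no stimulus: 55 in all.

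**Noise in one subject's change.** The documents give no baseline detection rate p, so 5-30% is assumed here. With no true change, SD = √(2p(1−p)/25) and the 95% limits are ±1.96 × SD:
- p = 5%: SD 6.2 points, limits ±12
- p = 10%: SD 8.5 points, limits ±17
- p = 20%: SD 11.3 points, limits ±22
- p = 30%: SD 13.0 points, limits ±25

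Dividing by √5 gives ±7 to ±11 points for a mean of 5 subjects at p = 10-30%. The formula uses one rate for all azimuths. Unequal rates with the same average would lower the binomial part, and session-to-session variation would raise the total.

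Exact binomial calculation over p = 5-50%: 36-44% of unchanged subjects show some gain, and 5-24% gain 12 points or more (3 of 25 trials).

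**Practice.** The mean bias equals the practice shift. Its size is not in the documents, so the following only illustrates it. Simulation (40,000 replicates) with no treatment effect, 15% detection and a 5-point session SD, using a paired t-test in place of the ANOVA, gives these rates of a significant gain (nominal 2.5%) for shifts of 0 / 5 / 10 / 15 points:
- single baseline, n = 5: 2.4% / 10% / 26% / 47%
- single baseline, n = 10: 2.5% / 20% / 57% / 88%
- second pre-training test as comparator, practice complete by then: about 2.5% throughout
- second test as comparator, practice half complete (shifts of 5 / 10 / 15 points): 5% / 9% / 15% at n = 5 and 8% / 18% / 32% at n = 10

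**What the repeat can estimate.** Under the same assumptions, the 95% half-width for the mean change from first to second baseline is about 15-17 points at n = 5 and 9-10 points at n = 10.

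**Second test alone or the average of both.** At p = 20%, averaging narrows one subject's limits to 1.96 × √(1.5 × 0.16 / 25) = ±19 points; the second test alone leaves them at ±22. If practice is complete by the second test, the average keeps half of the bias (5 points of a 10-point shift) and the second test alone keeps none.

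**Time for 55 trials.** The 30-trial VR progress test is given as 2 minutes in one section and 5 in another: 55/30 × 2 = 3.7 minutes, or 55/30 × 5 = 9.2 minutes. At the training pace of 200 trials in 30 minutes (9 seconds each) it is 55 × 9 / 60 = 8.3 minutes.

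**The case against.** The strongest reply is that the hoped-for effect is large. Going from near 0 to near 100% at 15°, 30° and 45° would add 15 of 25 trials, or 60 points, well beyond the noise limits. This stands for full recovery. A recovery confined to 15° is worth at most 5 of 25 trials, or 20 points, which lies inside the limits at a 20% or 30% rate and outside them at 5% or 10%.

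The plan also has safeguards: intact-side and no-stimulus trials in each frame test, fixation checks, injuries at least 6 months old, and a VR progress test after every session. They help, but the Analytical Plan does not use the intact-side or no-stimulus trials as a correction. The VR test is a secondary outcome, and it is first given after 200 training trials. Because no effect is expected before about two weeks, early VR results could describe practice on that test, but not on the frame test.

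A reader might infer more than the documents support:
- **That noise is counted as efficacy.** Eligibility does not depend on the baseline frame score, so noise adds no bias to the group mean, and the paired t-test above stays at its nominal rate with no practice shift. Noise matters for individual responder counts.
- **That the baseline is the subject's first contact with the device.** The sound localization and fixation screening earlier in session 1 uses the same frame. The baseline is the first field test on it.
- **That no retest without training exists.** The frame test is repeated at 3 and 6 months. Those retests inform within-subject variability, but they follow treatment, any fading of the effect is mixed in, and they cannot show early practice.

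The study is openly exploratory, which limits the severity. But its estimates are meant to feed later designs, and an unmeasured practice gain would carry over into them.

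**Conclusion.** The point holds for the frame test. With one pre-training administration and no control, a practice gain of any size adds in full to the estimated effect, and the plan has no pre-training measure of it. For individuals, binomial noise alone gives limits of about ±17 to ±25 points at an assumed unchanged rate of 10-30% (about ±12 at 5%), and nothing in the plan says what change counts as real. The detection rates, practice shifts and session SD are assumptions, so the false-positive rates show direction and rough scale only.

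It would also be too strong to say that a second baseline measures practice and settles the efficacy question. With 5 to 10 subjects the estimate is good to about ±9 to ±17 points. It reflects first-retest practice, not learning over the training month or expectation. It leaves HVF, the other primary measure, untouched. This is a cheap improvement that should be made, not a substitute for a control arm.

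**What to change.** - Repeat the peripheral frame test on campus at the start of session 3, before any training trial.
- Prespecify that second test as the comparator in the before/after analysis, with the average of the two baselines as a sensitivity analysis. Do not choose between them from the data: a practice shift of moderate size would often go undetected with so few subjects.
- Report the session 1 to session 3 change and its retest SD as a rough estimate of untreated change. Count a subject as improved only if the gain exceeds the retest limits.
- Analyse the intact-side and no-stimulus trials already collected as checks on response bias.
- Describe Aim 1 as a preliminary estimate of change.

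**Cost.** About 4-10 extra minutes in session 3 for each subject, with no new visit, staff or device, and a softer aim statement. A repeat HVF would need a further optometrist visit of up to 1 hour and is not part of this proposal.

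### The planned precision at n=5 (0.35 on each side of 80%) cannot be attained: at most 0.20 is possible above 0.80, and suitable intervals reach 0.42 to 0.52 below it

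*Combined protocol and SAP*

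**What the plan says.** The Sample Size section sets recruitment and the hoped-for number of completers: "we will recruit a sample size of 10 hemianopia subjects in this study in hopes of having at least 5 participants complete all study sessions". It then gives one calculation. Its premise is "Assuming that 80% of subjects will have a successful result", and its result is that "using n=5 subjects will allow for estimation of a 95% confidence interval with width 0.35 units either side of the estimate".

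No interval method is named. The one reference attached to the sentence concerns hemianopia, judging by its title in the reference list, and does not look like a statistical source. The section describes the study as exploratory and says its data will inform incidence estimates for later research. It gives no power, test, null value or margin.

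The Analytical Plan mentions no confidence interval for a success proportion. The Outcome Measure(s) section lists no such proportion, and the Sample Size section does not define success.

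**The concern.** The sentence promises the same distance above and below an estimate of 0.80. Adding 0.35 to 0.80 gives 1.15, which no proportion can reach. The fault is therefore visible before any method is chosen.

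The lower side matters more in practice. When a small pilot is used to plan a later study, the lower limit shows how poor the true success rate could still be. If 0.35 is too short on that side, the plan overstates how firmly five subjects would exclude a low success rate. Because this is the only calculation behind the sample size, nothing else in the plan corrects the impression.

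**Working it through.** **Inputs, all from the Sample Size section.** Assumed success proportion p = 0.80, that is x = 4 of n = 5; two-sided 95% confidence, z = 1.96; stated half-width 0.35; 10 recruited.

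**Step 1: reproduce the stated figure.** The normal-approximation (Wald) half-width is

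z × √(p(1 − p)/n) = 1.96 × √(0.8 × 0.2/5) = 1.96 × 0.1789 = 0.3506.

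This rounds to 0.35, so the arithmetic is sound. Other symmetric variants do not give 0.35: Wald with continuity correction 0.451, t with 4 degrees of freedom 0.497 or 0.555 (divisor n or n − 1), and 90% Wald 0.294.

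**Step 2: what it implies.** The limits are 0.80 − 0.3506 = 0.449 and 0.80 + 0.3506 = 1.151. The largest possible upper arm is 1 − 0.80 = 0.20. The expected number of failures is 5 × 0.2 = 1, far too few for a normal approximation.

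**Step 3: suitable 95% intervals for 4 of 5.**

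- *Clopper-Pearson (exact):* lower limit is the 2.5% quantile of Beta(4, 2); upper limit is the 97.5% quantile of Beta(5, 1).
- *Jeffreys:* 2.5% and 97.5% quantiles of Beta(4.5, 1.5).
- *Wilson:* centre (p + z²/2n)/(1 + z²/n) = (0.8 + 0.384)/1.768 = 0.670; half-width z√(p(1 − p)/n + z²/4n²)/(1 + z²/n) = 1.96 × √(0.032 + 0.0384)/1.768 = 0.294.

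| Method | Limits | Below 0.80 | Above 0.80 | Total width | Lower limit overstated by |
|---|---|---|---|---|---|
| Plan (Wald) | 0.449 to 1.151 | 0.351 | 0.351 | 0.701 | – |
| Clopper-Pearson | 0.284 to 0.995 | 0.516 | 0.195 | 0.711 | 0.166 |
| Jeffreys | 0.371 to 0.977 | 0.429 | 0.177 | 0.606 | 0.078 |
| Wilson | 0.376 to 0.964 | 0.424 | 0.164 | 0.588 | 0.074 |

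Five further methods give lower arms inside the same range: Agresti-Coull 0.440, inversion of the exact binomial test 0.457, mid-P 0.466, logit 0.491, and Wilson with continuity correction 0.501.

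**Step 4: actual coverage at n = 5 and a true rate of 0.8.** The Wald interval contains 0.8 only when x is 2, 3 or 4, with probability 0.0512 + 0.2048 + 0.4096 = 0.6656. At x = 5, which has probability 0.8⁵ = 0.328, it collapses to the single point 1. The same sum gives 0.942 for Wilson and Jeffreys and 0.993 for Clopper-Pearson.

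**Step 5: if all 10 recruits contribute an outcome.** For 8 of 10 the exact interval is 0.444 to 0.975.

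**The case against.** The best reply is that nothing in the trial depends on this sentence. The study is exploratory, five is a hoped-for minimum out of ten, no success proportion is listed as an outcome, and later incidence estimates would come from the observed data. All of that stands, and it is why the point is minor.

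A second reply is that the total width is about right: 0.70 implied, against 0.71 exact and less by Jeffreys or Wilson. This also stands, so the plan should not be said to overstate precision in general. But the sentence claims a distance on each side, and that is wrong on both sides.

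A third reply is that the plan prints no limits, and truncating at 1 is common practice. It is true that 0.45 and 1.15 are inferred from the sentence. Truncation removes the impossible upper limit, but it also removes the claimed symmetry and leaves the lower arm at 0.35, too short by every method in the table. The truncated interval, 0.45 to 1.00, has width 0.55 and is narrower than all three alternatives.

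Finally, choosing the exact method is partly a preference. It over-covers here (99.3%) and gives the largest correction. Wilson or Jeffreys would repair the sentence equally well.

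**Conclusion.** The concern holds and is minor. The stated symmetric 0.35 is a correctly evaluated normal approximation used where it does not apply. The impossible upper arm (0.35 claimed, 0.20 available) needs no assumption about method. The size of the error below the estimate does depend on method: the implied lower limit of 0.45 should be 0.38 (Wilson), 0.37 (Jeffreys) or 0.28 (exact). These figures take the assumed 80% at face value as 4 of 5 successes. The error lies mainly in the false symmetry, not in the overall width. Sample size, primary analysis and decision rules are unaffected.

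**What to change.** Replace the precision sentence in the Sample Size section with, for example:

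> With 4 of 5 successes the exact (Clopper-Pearson) 95% CI is 0.28 to 0.995; with 8 of 10, if all 10 recruits contribute an outcome, it is 0.44 to 0.97.

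A named Wilson or Jeffreys interval with its asymmetric limits would also do. The exact method is suggested because its coverage does not fall below the nominal level; the price is conservatism. If a success proportion is later reported, use the same method as the planning sentence. No new line in the Analytical Plan is requested, since success is not defined and no such proportion is listed as an outcome.

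The cost is one sentence and no extra subjects. The only disadvantage is a less favourable stated lower limit, 0.28 in place of the implied 0.45.

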Peripheral Visual Field Test - Since the Humphrey visual field test only measures up to 30° in the periphery, an additional peripheral visual field test will be administered using a semi-circular frame device (fig. 1) set 50 cm in front of the subject with LED lights acting as visual stimulus, located at azimuths of 15°, 30°, 45°, 60°, and 75°, as well as a center fixation light. Lights will be presented at a random time with a fixation period between each trial and locations selected randomly. Subjects will be asked to fixate on the center fixation light while lights are presented at random locations at random times (0-1.5 seconds). Upon detecting a light, subjects will press a button. Subject responses will be used to determine how far in the periphery, up to 75°, a subject can see. The test will present a total of 5 trials at each location in both the intact and hemianopic side, as well as 5 trials with no stimuli.

This test uses the free-field frame device to position visual and auditory stimuli, in the form of LED lights and speakers, at different angles of the patient. The patient is asked to maintain visual fixation on a lit LED light straight ahead during the test. Speakers will play a brief burst of white noise from a random location 15° or 45° on either the left or right side. The subject will be asked to identify where the sound is originating from either verbally or using a button response pad. During this test, subjects' eyes may be videotaped or photographed. These recordings or photos will be reviewed by a member of the study team to confirm the subject is able to properly maintain visual fixation.

Figure 1: Free-field frame device

track rehabilitation progress. The test consists of 30 trials with visual stimulus presented either 15°, 30°, 45° in either the hemianopia field or the intact field at random time intervals.

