Study Session 35: 3 Month Post-Intervention Follow-up Tests (1 hour)

Subjects will complete a follow-up visit 3 months after the end of rehabilitation on the Wake Forest Baptist Medical Center campus. The follow-up visit will consist of a peripheral visual field test, and NEI VFQ-25 and VA LV VFQ-48 questionnaires.

Study Session 36: 6 Month Post-Intervention Follow-up Tests (1 hour)

Subjects will complete a final follow-up visit 6 months after the end of rehabilitation on the Wake Forest Baptist Medical Center campus. The follow-up visit will consist of a peripheral visual field test, and NEI VFQ-25 and VA LV VFQ-48 questionnaires.

Outcome Measure(s)

The primary outcomes for all participants will be the visual field measurements from Humphrey Visual Field and peripheral frame test, with comparisons made before (visits 1 and 2) and after treatment (visits 34 and 35 or visits 63 and 64).

Secondary outcome measures will include differences in quality of life questionnaire results from before (visit 1) and after treatment (visit 33 or 63) and changes in VR progress test results during the course of rehabilitation (visits 3-32 and 33-62 if a subject repeats rehabilitation).

Exploratory outcome measures will be collected in subjects with restored visual fields. The qualities of recovered visual field will be examined with visual acuity, color recognition, and shape recognition tests after rehabilitation (visit 33 or 63).

Analytical Plan

Results will be analyzed initially using descriptive statistics. The improvement of visual detections will be assessed by using a two-way ANOVA on the percentages of visual detections to stimuli presented in the hemianopic hemifield in the peripheral visual field tests before and after rehabilitation. Comparisons for subjects will be done using chi square tests for proportions, and t-tests or ANOVA procedures for continuous variables. Other inferential statistical analysis will be conducted as appropriate.

Human Subjects Protection

Subject Recruitment Methods

Protocol version: 2

Protocol updated 7.01.20

Subjects with homonymous hemianopia on either the left and right side of the visual field will be recruited using resources from Wake Forest University Health Sciences' Clinical and Translational Science Institute (CTSI). Members of the PI's research team will perform recruitment. Coordination of potential participants' visit will be done by phone or in person conversation or by email.

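### The peripheral-field part of the primary outcome counts raw button presses and makes no stated use of the blank trials, so looser pressing after training would score as improved vision

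*Combined protocol and SAP*

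**What the plan says.** The Outcome Measure(s) section names two primary measures: "The primary outcomes for all participants will be the visual field measurements from Humphrey Visual Field and peripheral frame test". Under Peripheral Visual Field Test, the scored response is a press, with no report of where the light was: "Upon detecting a light, subjects will press a button". On the trial count: "The test will present a total of 5 trials at each location in both the intact and hemianopic side". The same sentence then adds the blanks, given as "as well as 5 trials with no stimuli". Lights appear at five azimuths, at random times and locations.

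The Analytical Plan specifies a "two-way ANOVA on the percentages of visual detections to stimuli presented in the hemianopic hemifield", before against after rehabilitation. Neither section says what is done with the blanks. No correction, false-press limit, repeat-test rule, response window or before/after comparison of blank presses is given.

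Between the two tests, subjects train on 200 trials a day for a month and press when they detect a stimulus. The Interventions section says of that training: "The design of the fixed, predictable timing and 9:1 ratio will help subjects shift their attention to the blind field". No blank training trials are described. The Design section compares subjects only with their own pre-intervention measures.

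**The concern.** A yes/no press mixes two things: whether the subject saw the light, and how willing the subject is to press when unsure. Blanks exist to separate the two, and here they are collected but not used. After a month of expecting stimuli on the blind side and pressing for them, a subject could plausibly press more freely. In the test, 50 of 55 trials contain a light, so free pressing is rarely exposed. Without a control group, a change in pressing habit and a change in vision both appear as a before/after rise. The results are meant to inform the design of later studies, so an artefact of this kind would carry forward as an apparent treatment effect.

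**Working it through.** **Inputs from the documents.** 5 azimuths x 5 trials = 25 lights per side per test; 5 blanks per test; 10 recruited, at least 5 completers hoped for. Pooled blanks per visit: 5 x 5 = 25 for 5 completers, 10 x 5 = 50 for 10 subjects.

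**Assumptions.** False-press rates of 5% before and 20% or 30% after training; the documents give none. The false-press rate on blanks equals that on unseen lights. Trials are independent. Tests are two-sided at 0.05, since the plan states no level.

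**The plan's own precision figure.** Under Sample Size, 1.96 x sqrt(0.8 x 0.2 / 5) = 0.351, which reproduces the stated 0.35. It concerns the proportion of successful subjects and does not bear on false presses.

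**Effect on the score.** Expected raw score = s + (1-s)f, where f is the false-press rate. If f rises by d and s is unchanged, the score rises by (1-s)d.
- s = 0, 5% to 20%: 15 points. 5% to 30%: 25 points.
- s = 0.2, 5% to 20%: 0.8 x 15 = 12 points.

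**Effect on the test.** Simulation with 5 subjects, vision unchanged, the same shift in everyone, and a time-by-location ANOVA without a subject term (one reading of the plan), with a paired t-test beside it. Share of runs with a significant time effect:

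| True detection | False presses | ANOVA | Paired t |
|---|---|---|---|
| 0 | no shift (5%) | 5% | 4% |
| 0 | 5% to 20% | 95% | 79% |
| 0 | 5% to 30% | over 99% | 98% |
| 10% | 5% to 20% | 73% | 53% |

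**What 5 blanks show for one subject.**
- Upper one-sided 95% limit after 0/5: 1 - 0.05^(1/5) = 45%. After 0/25: 1 - 0.05^(1/25) = 11%.
- Chance of no blank press at a true 20% rate: 0.8^5 = 33%. With 25 blanks: 0.8^25 = 0.4%.
- Starting from 0/5, Fisher's exact test reaches p < 0.05 only at 4/5 or more (p = 0.048).

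**What pooled blanks show.** Exact Fisher power for a before/after shift:

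| Blanks per visit | 5% to 20% | 5% to 30% |
|---|---|---|
| 25 (5 completers, as planned) | 20% | 55% |
| 50 (10 subjects, as planned) | 51% | 90% |
| 125 (5 completers, 25 blanks each) | about 95% | over 99% |

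**Noise in the corrected score.** (H-FA)/(1-FA), with H the press rate on lights and FA that on blanks, has target value s. With s = 0 and 25 lights, its SD at one visit is about sqrt[f(1-f)(1/25 + 1/blanks)]/(1-f). With 25 blanks this is 0.065 at f = 5% and 0.141 at f = 20%, so the SD of one subject's change is sqrt(0.065^2 + 0.141^2) = 0.156, about 16 points. With 5 blanks the approximation breaks down; simulation gives about 42 points.

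**The case against.** Several points on the other side stand.

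- **Other checks exist.** A reader might infer that nothing in the study could reveal a pressing shift. The documents do not support that. The blanks are recorded at each frame test, Humphrey is the other primary measure, and subjects whose field expands take shape-naming, colour-naming and grating tests, where looser pressing would not produce correct answers. But Humphrey reaches only 30° and has no stated false-positive rule, and the naming and grating tests are exploratory and post-treatment only. A pure pressing shift should also raise all five azimuths about equally, but recovery of the whole hemifield, as reported in the animals, could look similar.
- **Training does not reward pressing.** That is another tempting inference. Food reward is described only for the cats. In the human training, the timing and the 9:1 ratio are meant to shift attention, and subjects are told to press on detection. A looser criterion is plausible but not documented. The random timing in the test also limits carry-over of anticipation.
- **Five blanks per test are not hopeless at group level.** With all 10 subjects, pooled power for a 5% to 30% shift is 90%. That falls to 55% with the 5 completers hoped for, and the plan specifies no such comparison.
- **Correction is not a cure.** The corrected score is zero for a blind subject only on average. Even with 25 blanks, one subject's change has an SD about as large as the 15-point bias.
- **The study is exploratory** and begins with descriptive statistics. This lowers the severity but does not alter how the score behaves.

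**Conclusion.** The point holds as a gap in the analysis with a quantified risk. It does not show that bias will occur. As written, any rise in false presses passes into the peripheral-field outcome at (1-s) times its size, and no stated analysis would separate it from recovered vision. The 15-25 point range rests on assumed false-press rates and no residual vision, and it shrinks in proportion as true detection rises. The simulated significance rates also assume the same shift in every subject; uneven shifts would lower them. The finding that 5 blanks are too few is firmest per subject. Pooled, they are weak for a moderate shift with 5 completers and adequate only for a large shift with all 10. The pooled counts assume every subject counted takes the frame test at both visits. In an exploratory study this is a change that should be made, not one on which the study depends.

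**What to change.** 1. Raise the blanks from 5 to about 25 per frame test, interleaved at random, at the baseline, post-treatment and both follow-up tests.
2. State in the Analytical Plan that false-press rates will be reported by subject and visit and compared before and after training.
3. Pre-specify (H-FA)/(1-FA) per subject and visit, including how FA = 1 is handled, and present it beside the raw percentage.
4. Claim improved detection on this test only if the gain persists after correction.

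**Cost.** Twenty more trials per test, about 1-2 minutes if each takes 3-5 seconds (an assumption: 20 x 3 = 60 s, 20 x 5 = 100 s), and a short addition to the analysis text. The corrected score is noisier than the raw one, with an SD of about 16 points for one subject's change, or about 16/sqrt(5) = 7 points for the mean of 5 completers. Corrected gains may be less favourable. Twenty-five blanks still will not settle a moderate shift within one subject; the benefit is mainly in the pooled comparison. If blanks cannot be added, steps 2 and 3 still apply to the existing 5, with the imprecision stated.
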